
Statistical Methods and Analyses
	
Endpoints will be described and compared between baseline and day 10, for the treatment group using cross-tabulation tables and Fisher's Exact test for categorical variables, t-test for normally distributed continuous variables, and Wilcoxon non-parametric test for non-normally distributed continuous or ordinal variables. Data collected will be compared with a retrospective analysis of age-matched Ebola-infected individuals who presented with similar symptoms (and viral loads) and who did not receive IFN <math>\beta</math>-1a.

	
Safety variables such as fever will be considered in three different formats:
 

1. As ordinal, representing various levels of severity of the AE. For instance, fever will be described as “none”, “mild”, “moderate” or “severe”.

2. As binary, considering only the presence vs. the absence of the AE.

3. As binary, considering the most serious expression of the AE. For instance by grouping “moderate” and “severe” together.

 
Separate analyses for time periods of 0-3, 4-7 and 8-10 days will be conducted. For each of these time periods the most severe report of the AE for each participant will be counted.
 
Adverse Events and Serious Adverse Events will be considered in two ways: presence of any event and presence of any event related to the treatment.
 
Viral clearance and symptom endpoints will be analyzed as binary variables for detection (presence) or non-detection (absence) as well as continuous variables where applicable (e.g.; quantitative RT-PCR measurements).

--	---

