### **5. Study Design**

This study is single-arm clinical trial with a pre- and post- study design. The study will include patients who are admitted with EBOV infection to a treatment centre. If a patient meets the inclusion criteria and gives informed consent (or informed consent is given by a substitute decision maker who is responsible for the patient due to the patient's illness), the patient will be enrolled into the study i.e. the first 30-50 eligible patients will be enrolled. Patients who receive IFN  $\beta$ -1a will be treated through the Special Access/Compassionate Release Program (consent to treatment through their treating physician) administered in Conakry, Guinea. This part of the study will collect data retrospectively, including results from research testing of (residual/to be discarded) blood samples. The study team can make available the systematic data collection forms to the treating physician to help in monitoring of adverse events and effect of therapy, enabling more specific reporting to the Special Access Program administered in Conakry, Guinea by the treating physician for patients receiving IFN  $\beta$ -1a.

As noted above, retrospective data collection will include patients with EBOV disease who do not participate in this clinical trial. Data from IFN  $\beta$ -1a-treated patients will be matched with data from patients who did not receive IFN  $\beta$ -1a, based on age, sex, estimated days post-onset of symptoms, and viral load (if available). This data collection is similar to that proposed in this protocol. Also, this protocol proposes to test blood collected clinically (residual or to be discarded) for comparisons between the groups in this interventional study.

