### **Pre- and post- Clinical Trial:**

The authority to approve a treating physician's access to IFN  $\beta$ -1a for treatment of patients under the Special Access Program, is based on a medical decision for treatment and a discussion between the treating physician and the patient (or the patient's substitute decision maker). The collection of safety and efficacy data for monitoring by the treating physician and reporting to [name] can be done based on the study case report. This will facilitate reporting by the treating physician and allow more specific and consistent reporting to [name].

This component of the study is to provide the ability to have special access to IFN  $\beta$ -1a if indicated clinically while providing consistent monitoring of adverse events and effect of therapy. Considering that some patients may continue to deteriorate despite antivirals or that they may be infected with an antiviral resistant strain, IFN  $\beta$ -1a will be made available to treating physicians for patients for whom the treating physician believes that there may be a benefit to giving IFN  $\beta$ -1a. Consent for treatment with IFN  $\beta$ -1a would be obtained by the treating physician. Monitoring of treatment will be important to ensure that any safety concerns are identified. Monitoring will include collecting information from the patient's chart as well as some research testing of residual samples which would otherwise be discarded. A template of the informed consent form is attached. The comparison group will be the group of patients who have EBOV disease and do not receive IFN  $\beta$ -1a.

Of note, it is recognized that there will likely be missing data on study participants due to retrospective data collection. Collection of data will be based on the clinical course and interventions required in the care of these patients.

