**5.3 Inclusion Criteria**

Only potential patients fulfilling all of the following criteria are eligible for enrolment in this interventional trial.

1. Able to provide informed consent. Substitute decision maker may provide informed consent in cases where the patient is ill and unable to provide informed consent.
2. Aged  $\geq 18$  years and  $< 70$  years of age on the day of inclusion.
3. Is admitted to the treatment centre.
4. Suspect, probable or confirmed EBOV infection as defined above.
5. Symptoms onset  $< 4$  days
6. Is able to comply with all trial procedures.

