### **6.1 Informed Consent Process**

#### **Clinical Trial:**

All participants (or substitute decision makers) must understand and sign the informed consent document. The Guinean physicians and associated health workers will play an important role in addressing cultural and ethical sensitivities associated with the treatment protocol, and the Guinean authorities have indicated they will assume responsibility for disseminating information about the nature of clinical trials aimed at treating Ebola virus disease.

The observational part of the study will collect data retrospectively, and results from research testing of (residual/to be discarded) blood samples and respiratory secretions.

The comparison group for this part of the study will in part be the population that may be included in an existing epidemiologic study for which there is a waiver of consent. For patients

in the comparison group who were not enrolled in such a study where waiver of consent was applied, all reasonable efforts will be made to obtain informed consent where that individual's data will be used. However, it should be noted that obtaining informed consent from a non-IFN  $\beta$ -1a-treated patient who survived the ebola infection and left the clinic may be difficult to obtain, as it may be from the relatives of those non-IFN  $\beta$ -1a-treated patients who died following ebola infection. Retrospective data collection and testing will be as consistent as possible with the clinical trial data collection form, depending on data available from medical records. Research testing will be performed on the blood and secretions samples (residual or to be discarded).

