## 10.2 Statistical analyses and methods

Demographics, and underlying conditions will be described by means and standard deviation for continuous variables, by median and interquartile range for ordinal or count variables, and by frequencies and percentages for categorical variables. Endpoints will be described and compared between treatment and usual standard of care groups using cross-tabulation tables and Fisher's Exact test for categorical variables, t-test for normally distributed continuous variables and Wilcoxon non-parametric test for non-normally distributed continuous or ordinal variables.

Safety variables such as fever will be considered in three different formats:

1. As ordinal, representing various levels of severity of the symptom. For instance, fever will be described as "none", "mild", "moderate", or "severe".
2. As binary, considering only the presence vs. the absence of the symptom.
3. As binary, considering the most serious expression of the symptom. For instance by grouping "moderate" and "severe" together.

Separate analyses for time periods of 0-3, 4-7, and 8-10 days will be conducted. For each of these time periods the most severe report of the AE for each participant will be counted.

Adverse Events and Serious Adverse Events will be considered in two ways: presence of any event and presence of any event related to the treatment.

Symptoms will be assessed as a repeated measure using GEE modelling.

Survival will be analyzed using a Kaplan-Meier curve and Cox-proportional hazard modeling with 2 week and 1 month survival rates determined.

Viral clearance will be analyzed as binary variables for detection (presence) or non-detection (absence) as well as continuous variables where applicable (e.g. quantitative RT-PCR measurements).

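### The synopsis and Section 5 match the untreated comparators on different variables, and the other descriptions of the group do not mention matching, so the between-group contrast is not fixed

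*Protocol*

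**What the plan says.** Section 5 sets the design: "This study is single-arm clinical trial with a pre- and post- study design". Untreated patients enter through retrospective data collection, and the protocol describes them in five places.

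- **Synopsis, Statistical Methods and Analyses:** treated patients are compared with a "retrospective analysis of age-matched Ebola-infected individuals who presented with similar symptoms (and viral loads").
- **Section 5, Study Design:** treated and untreated data are matched "based on age, sex, estimated days post-onset of symptoms, and viral load (if available").
- **Section 5, Pre- and post- Clinical Trial:** "The comparison group will be the group of patients who have EBOV disease and do not receive IFN" β-1a. Matching is not mentioned.
- **Section 6.1:** "The comparison group for this part of the study will in part be the population that may be included in an existing epidemiologic study" that has a waiver of consent. Matching is not mentioned.
- **Section 10.2:** "Endpoints will be described and compared between treatment and usual standard of care groups using cross-tabulation tables" with Fisher's exact test, a t-test or the Wilcoxon test. Matching is not mentioned.

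Section 5.3 limits treated patients by time since onset ("Symptoms onset" under 4 days). No such limit is stated for comparators.

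**The concern.** With one treated arm, the untreated group is the only source of between-group evidence. It is used for adverse event and SAE frequencies (Sections 8.4 and 9.2), clinical improvement and death (Section 9.3), and the group comparisons in Section 10.2. Section 16 makes extension to 100 participants, and a possible larger study, depend in part on whether the treated patients appear to do better than those on standard care.

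Comparator records are collected retrospectively, so outcomes may already be known when matches are chosen. Two different lists then leave a choice of comparators open after the fact.

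Days since onset is the difference that matters most. Section 5.1 itself says that earlier treatment may be more useful than later treatment. A comparator first seen late in illness has survived the earlier days, may be sicker on arrival, and is at another point of the viral load course. Without alignment on illness day, the contrast mixes any drug effect with stage of illness.

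**Working it through.** **1. The two lists side by side**

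| Variable | Synopsis | Section 5 |
|---|---|---|
| Age | yes | yes |
| Sex | no | yes |
| Days since onset | no | yes (estimated) |
| Viral load | yes, in parentheses | yes, where available |
| Presenting symptoms | yes | no |

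Age is the only variable that both lists require without qualification. Viral load is in both, but Section 5 makes it conditional. Sex and days since onset are only in Section 5, and symptoms only in the synopsis. The two lists can therefore select different comparators from the same records.

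**2. How far the choice could move a mortality contrast**

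The protocol gives no figure to reproduce, because its sample of 30-50 is a feasibility number (Section 10.1). What follows is illustration, with an inert drug and all treated patients early in illness.

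*Mixed pool, either direction.* Spurious difference = s × (m_early − m_late), where s is the share of comparators first seen late. All inputs are assumptions: s = 30-70%, m_early = 50-60%, and m_late 10 to 15 points higher or lower. The level of m_early cancels.

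- Smallest: 0.3 × 10 = 3.0 points.
- Largest: 0.7 × 15 = 10.5 points.
- With exact alignment on days since onset: 0.

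*Survivorship only.* Remaining fatality = F(1 − q)/(1 − Fq). F is overall fatality, 57-90% in Section 1.1. The share of deaths before a late comparator is first seen, q, is assumed to be 40%.

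- F = 0.57: 0.342/0.772 = 44.3%, a shift of 12.7 points.
- F = 0.70: 0.420/0.720 = 58.3%, a shift of 11.7 points.
- F = 0.90: 0.540/0.640 = 84.4%, a shift of 5.6 points.

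These shifts apply only if every comparator is late. If 30-70% are late (assumed), they become 0.3 × 5.6 = 1.7 to 0.7 × 12.7 = 8.9 points. The direction, against IFN β-1a, is built into this model.

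*Sex, absent from the synopsis list.* An assumed mortality gap of 5-10 points times an assumed imbalance of 10-20 percentage points gives 0.05 × 0.10 = 0.5 points to 0.10 × 0.20 = 2 points.

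**3. Scale**

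At 50% mortality and equal groups (both assumed), the standard error of a difference is √(2 × 0.25/n): 12.9 points for n = 30 and 10.0 points for n = 50. The choice of list could thus move the estimate by up to about one standard error.

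**The case against.** A reader might infer a third rule, that all untreated patients form the comparison group with no matching. The text does not say so. The trial description follows the matching statement within Section 5, so it can be read as naming the pool from which matches are drawn. Section 10.2 is likewise only silent, and a statistical analysis plan may settle matching ratios, calipers and paired methods. This objection stands. The contradiction is between two lists, and the remaining places merely fail to point to either.

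Section 6.2 also weakens the concern. It records day of illness at baseline and has follow-up compared on that basis for treated and untreated patients alike. The body of the protocol thus plans for illness day, and only the synopsis list omits it. However, Section 6.2 does not say which patients are selected as comparators.

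The synopsis list is not blind to stage either. Similar symptoms and similar viral loads would align it in part, and the illustrations give no credit for that. Death is a tertiary endpoint, no effect on the primary viral load endpoint is quantified, and a pilot of this size is imprecise anyway. All of this limits the size of the problem. None of it reconciles the lists.

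**Conclusion.** The protocol contradicts itself on how its only comparison group is matched, and this should be settled before comparators are selected. It does not prevent the pilot from running. Until it is settled, the between-group contrast depends on which list is applied.

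The size and direction of any bias cannot be derived from the protocol. Under the stated assumptions, the illustrations give a few to about 10 points in mortality, in either direction. A reader might infer from the survivorship formula a firm shift of 6 to 13 points against IFN β-1a. The documents do not support that. It requires every comparator to present late, a share of early deaths with no source in the protocol, and late presenters who fare better rather than worse.

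**What to change.** - State one matching rule, in the same words, in the synopsis and Section 5. Keep the Section 5 list: age, sex, days since onset, and viral load where available.
- Decide explicitly whether presenting symptoms are part of the rule.
- In the Section 5 trial description and in Section 10.2, name that matched set as the comparison group. Label any comparison with all untreated patients as descriptive only.
- State that matches are selected from day-1 data without reference to outcomes.

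Viral load should stay conditional. Sections 5 and 6.5 expect missing data, and Section 6.2 makes baseline tests depend on resources. With 30-50 patients, each further mandatory variable makes matching harder.

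The cost is protocol wording. The downside is that some treated patients may have no close match, and the protocol gives no basis for saying how many.

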### **Pre- and post- Clinical Trial:**

The authority to approve a treating physician's access to IFN  $\beta$ -1a for treatment of patients under the Special Access Program, is based on a medical decision for treatment and a discussion between the treating physician and the patient (or the patient's substitute decision maker). The collection of safety and efficacy data for monitoring by the treating physician and reporting to [name] can be done based on the study case report. This will facilitate reporting by the treating physician and allow more specific and consistent reporting to [name].

This component of the study is to provide the ability to have special access to IFN  $\beta$ -1a if indicated clinically while providing consistent monitoring of adverse events and effect of therapy. Considering that some patients may continue to deteriorate despite antivirals or that they may be infected with an antiviral resistant strain, IFN  $\beta$ -1a will be made available to treating physicians for patients for whom the treating physician believes that there may be a benefit to giving IFN  $\beta$ -1a. Consent for treatment with IFN  $\beta$ -1a would be obtained by the treating physician. Monitoring of treatment will be important to ensure that any safety concerns are identified. Monitoring will include collecting information from the patient's chart as well as some research testing of residual samples which would otherwise be discarded. A template of the informed consent form is attached. The comparison group will be the group of patients who have EBOV disease and do not receive IFN  $\beta$ -1a.

Of note, it is recognized that there will likely be missing data on study participants due to retrospective data collection. Collection of data will be based on the clinical course and interventions required in the care of these patients.

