Methodology/Trial Design:	This is a Phase I/II, interventional trial designed to assess the safety and trends in clinical course of Ebola virus disease in patients $\geq 18$ and $< 70$ years of age treated with either IFN $\beta$ -1a and usual supportive care, or usual supportive care only. It is associated with appropriate monitoring of therapy.
Planned Sample Size:	Pilot: 30-50
Treatment and Specimen Collection Schedules and Duration of Follow-up:	Subcutaneous injection of IFN $\beta$ -1a daily for up to 10 days. Up to 11 blood samples will be drawn on days 1-10 and one month after discharge from the treatment centre. Subjects will be followed for the duration of their stay in the treatment centre. From first patient enrolment to last patient last visit, it is expected that the study will last 4 months.
Investigational Product:	Recombinant IFN $\beta$ -1a; an injectable sterile suspension with licensed IFN- $\beta$ provided in single use syringes
Form:	Sterile, clear, colorless preservative-free liquid, single-use syringe
Composition:	Each 0.5 mL of 60 microgram (mcg)/mL of IFN $\beta$ -1a in a pre-filled glass syringe contains 30 mcg of IFN $\beta$ -1a, 0.79 mg of sodium acetate trihydrate USP; 0.25 mg of glacial acetic acid USP; 15.8 mg of arginine hydrochloride USP; and 0.025 mg Polysorbate 20 in water for injection, USP to a pH of about 4.8.
Route:	Subcutaneous (sc) injection - undiluted
Lot Number:	V32482
Inclusion Criteria:	
Only potential patients fulfilling all of the following criteria are eligible for trial enrolment:
 
 
1. Able to provide informed consent. Substitute decision maker may provide informed consent in cases where the patient is ill and unable to provide informed consent.
 
2. Aged <math>\geq 18</math> years and <math>< 70</math> years of age on the day of inclusion.
 
3. In the treatment centre.
 
4. Suspect, probable or confirmed Ebola virus infection as per case definitions.
 
5. Symptom onset <math>< 4</math> days.
 
6. Able to comply with trial procedures.
 
 
The treating physician is responsible for recommending and for initiating therapy with IFN <math>\beta</math>-1a through the Special Access/Compassionate Release Program.

Exclusion Criteria:	A potential subject fulfilling any of the following criteria is to be

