**Favipiravir** (T-705) (Medivector/Toyma/Fuji) is a small molecule, viral polymerase inhibitor that has been conditionally approved in Japan for influenza virus infection. Published *in vitro* and mouse model studies suggest that the drug is anywhere from 10-60 fold less effective against EBOV than influenza virus. Pilot nonhuman primate studies are underway with anticipated higher dosing. Up to 15,000 treatment courses are currently available, with a projected 100,000 treatment courses to be available in 3 months. It is anticipated that 90 tablets are required over 5 days for human treatment course. Given the high incidence of nausea, vomiting and diarrhea in EBOV-infected individuals, this oral bioavailability presents a significant concern.

**BCX4430** (BioCryst Pharmaceuticals, Inc.) is a small molecule, viral polymerase inhibitor. Efficacy has been demonstrated *in vitro* and in mouse models of EBOV disease. Nonhuman primate studies are anticipated to begin shortly. A preclinical IND submission is anticipated in November 2014, with potentially 2000 treatment courses projected to be available in March 2015.

**Brincidofovir** (CMX001) (Chimerix) is a small molecule, viral polymerase inhibitor that has demonstrated *in vitro* antiviral activity against filoviruses. Because of metabolism differences its evaluation in Macaque nonhuman primates is precluded. Phase 3 studies in >1000 trial subjects have been conducted against CMV and adenovirus infections. Potentially there are 3,500 treatment courses currently available. Oral bioavailability given nausea, vomiting, and diarrhea is a concern for the 6-10 tablet treatment course.

**Coagulation related interventions** Recombinant nematode anti-coagulant protein C2 that blocks Factor X cleavage has completed Phase 2 trials. The drug exhibits 33% efficacy when initiated 24 hours after infection in nonhuman primates. 100 doses are currently availability, dependent on ongoing stability testing. Drotrecogin alfa was approved for the treatment of severe sepsis, but has been withdrawn. Nonhuman primate studies showed 18% treatment efficacy when administered <6 hours after infection. Availability is unknown.

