**5.4 Exclusion Criteria**

A potential patient fulfilling any of the following criteria is to be excluded from study enrolment:

1. Known hypersensitivity to interferon beta preparations
2. Pregnancy (the use of IFN  $\beta$ -1a is associated with abortifacient effects in rhesus monkeys and may cause miscarriage in humans)
3. Chronic liver disease with synthetic dysfunction and/or decompensation (ascites, hepatic encephalopathy, history of bleeding esophageal or gastric varices)
4. Moderate to Severe congestive heart failure, grade III or grade IV LV function
5. Previous history of serious psychiatric illness (e.g., psychosis, suicide, depression requiring hospital admission)

6. History of severe autoimmune disease (systemic lupus erythematosus, thyroiditis, vasculitis)

For this interventional study, the exclusion criteria can be reviewed, by the treating physician, to assess the potential risks of therapy.

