### 6.4 Concomitant Medication

All concomitant medication should be appropriate as determined by the treating physician and should be documented in the CRF. For instance, at the discretion of the treating physician, broad-spectrum antibiotics may also be given to cover possible superimposed bacterial infections.

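### The protocol defines the comparison group in two incompatible ways, and its rules let other experimental anti-Ebola agents into either group of the viral-RNA contrast

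*Protocol*

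**What the plan says.** The synopsis (Methodology/Trial Design) describes patients given interferon "and usual supportive care, or usual supportive care only". Section 10.2 likewise compares the treated patients with a usual standard of care group.

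Section 5 (Pre- and post- Clinical Trial) uses a different definition: "The comparison group will be the group of patients who have EBOV disease and do not receive IFN" β-1a. It attaches no condition about other treatment. The same text explains access to interferon partly on the ground that "some patients may continue to deteriorate despite antivirals or that they may be infected with an antiviral resistant strain".

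Section 5 matches treated to untreated patients on age, sex, days since symptom onset and, where available, viral load. The synopsis names age, symptoms and viral load. Neither list includes co-treatment. The six exclusion criteria in section 5.4 begin with "Known hypersensitivity to interferon beta preparations", and none concerns another anti-Ebola agent. The inclusion criteria in section 5.3 do not mention one either. Section 6.4 states: "All concomitant medication should be appropriate as determined by the treating physician and should be documented in the CRF". The two-group endpoint tests named in section 10.2 (Fisher, t-test, Wilcoxon) are unadjusted.

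**The concern.** The primary endpoint is reduction or clearance of viral RNA, which is what other anti-Ebola antivirals are meant to change. Interferon is given at the treating physician's judgement and the comparators are found retrospectively, so nothing in the design balances use of such agents.

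More use among treated patients would be credited to interferon. More use among comparators would hide an interferon effect. The within-patient comparison of baseline with day 10 is exposed too, because another agent started in that window would be counted as interferon's effect.

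Under section 16 the pilot's results, including any trend toward efficacy against standard of care, feed the decision on extending to 100 participants.

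**Working it through.** The protocol gives no figure to reproduce. Section 10.1 chooses 30–50 patients for feasibility and states no alpha, power, effect or standard deviation. The check is therefore textual first, with an illustrative calculation after it.

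**Text.** Take a patient with Ebola virus disease who receives another experimental anti-Ebola agent and no interferon. Section 5 counts this patient as a comparator; the synopsis does not, because the care is more than supportive. Now take an interferon patient who is also on another agent. Sections 5.3, 5.4 and 6.4 admit this patient, and section 5 foresees the possibility. Neither matching list separates these patients from unexposed ones, and the named tests have no term for co-treatment.

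**Size.** Let p_T and p_C be the shares using another agent in the treated and comparison groups, and d the log10 reduction in viral load that the agent causes. If effects add on the log10 scale:

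apparent interferon effect = true effect + (p_T − p_C) × d

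Assumptions not in the protocol: d = 1 log10; 30 or 50 patients in each group (the number of comparators is not stated); SD of the log10 change 1.0–2.0; two-sided alpha 0.05; independent groups; no true interferon effect. With b the absolute bias and se = SD × √(2/n), the false-positive rate is Φ(b/se − 1.96) + Φ(−b/se − 1.96).

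Example: a 25-point difference gives b = 0.25 × 1 = 0.25. With n = 30 and SD 1.0, se = 1.0 × √(2/30) = 0.258 and b/se = 0.968. The rate is Φ(−0.992) + Φ(−2.928) = 0.1606 + 0.0017 = 0.162.

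| Difference in use | Bias (log10) | False-positive rate, n = 30 | False-positive rate, n = 50 |
|---|---|---|---|
| 0 points | 0 | 0.05 | 0.05 |
| 10 points | 0.10 | 0.05–0.07 | 0.06–0.08 |
| 25 points | 0.25 | 0.08–0.16 | 0.10–0.24 |
| 50 points | 0.50 | 0.16–0.49 | 0.24–0.71 |

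Each range runs from SD 2.0 (low end) to SD 1.0 (high end).

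**Masking.** Suppose a true interferon effect of 1.0 log10 with SD 1.5, and comparators using the agent 50 points more often. The apparent effect is 1.0 − 0.5 = 0.5 log10. Power falls from 0.733 to 0.252 with n = 30, and from 0.915 to 0.385 with n = 50.

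**The case against.** The strongest reply is that other agents were probably little used. Section 1.2 says that no specific approved treatment exists and that patients currently get supportive care only. A reader might infer from section 1.4, for instance "Up to 15,000 treatment courses are currently available" for favipiravir, that the protocol expects such use. It does not say so. That section surveys candidates and does not describe use in Guinea; some had no product available, and oral dosing is called a concern for favipiravir and brincidofovir. Section 5 says only that patients may deteriorate despite antivirals. Entry within 4 days of onset, with most patients treated within 24 hours of admission, leaves little time for an earlier antiviral to fail. This limits the likely size. It does not remove the contradiction, because section 1.2 describes November 2014 and is not a rule of the trial.

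A second reply is that baseline and daily medication is recorded (sections 6.4 and 6.5), so an analysis plan not shown here could adjust for it. That is partly right. But the comparator definition and the matching factors are already set in the protocol, and section 6.1 makes comparator data depend on medical records. A reader should not assume that co-medication is reliably recorded in both groups.

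A third reply is that this is a feasibility pilot whose comparison is already non-randomised and retrospective. That bears on the grade. The primary objective is nonetheless the effect on viremia.

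**Conclusion.** The contradiction is real. The synopsis and section 10.2 describe a comparator on supportive or standard care, while the section 5 definition and matching factors admit patients on other experimental agents to either group.

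The size cannot be determined from the protocol. At d = 1 log10 the bias runs from about 0, if use is rare or equal, to 0.5 log10 at a 50-point difference; it scales in proportion to d. Both the difference in use and d are assumptions. At a 10-point difference the false-positive rate stays at 0.05–0.08, close to nominal.

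A reader might conclude that the efficacy comparison is certainly and materially biased, or that the trial cannot proceed without this change. The documents support neither, because they report no actual use of another agent. This is a point that should be fixed.

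**What to change.** 1. Reword the comparator in section 5 so that it agrees with the synopsis and section 10.2, and reconcile the mention of patients already on antivirals with that definition.
2. State in section 5 that the main efficacy comparison includes, in both groups, only patients with no documented experimental anti-Ebola agent (antiviral, antibody, siRNA or oligonucleotide, convalescent plasma or serum) before day 1. Use the medication record for treated patients and the chart for comparators.
3. Report by group any such agent started on days 1–10, with a sensitivity analysis. Do not match on it: it is post-baseline and can depend on response to treatment and on surviving long enough to receive it, so matching could itself introduce selection bias.
4. Report exposed patients separately and keep them in the safety data.

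The change is mostly wording. It costs some patients or matches in a study of 30–50, and its reliability for comparators depends on how complete the charts are. It defines an analysis set and does not limit what physicians may give.
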